## 9.10 Pharmacokinetic Analyses

Measured plasma concentrations of lefamulin and BC-8041 will be summarized descriptively by treatment group and time point of collection. Summary statistics in the tabulation will include  $n$ , mean, standard deviation, CV [%], median, minimum and maximum.

Population PK modeling will be used to determine the individual model-predicted concentrations of lefamulin at least for Day 1 (PK/PD analysis). Additionally, plasma concentration time curves will be generated for day of IV/PO switch and PO treatment only. Simulation of model output will enable descriptive statistical analysis of PK variables such as the  $C_{max}$ ,  $C_{min}$  and AUC for lefamulin.

A description of the population PK analysis will be described in a separate SAP. Results of this analysis will be reported separately.

## 9.11 Health Utilization Variables and Patient Reported Outcome

Exploratory evaluation of a variety of health utilization variables (e.g., length of hospital stay, duration of antibiotic therapy, discharge status, discharge destination) as well as a PRO instrument (SF-12) will be performed. Details for this exploratory analysis will be presented in a separate SAP and results will be presented in a stand-alone clinical study report

# 10 STUDY MONITORING

## 10.1 Clinical Monitoring

All aspects of the study will be carefully monitored by the Sponsor's authorized individuals, acting as agents of the sponsor with respect to current Good Clinical Practice and Standard Operating Procedures for compliance with applicable government regulations. These individuals will have access to all records necessary to ensure integrity of the data and will periodically review the progress of the study with the principal investigator.

Frequent communication between the study site and the Sponsor is essential to ensure that the subject safety is monitored adequately. The Investigator will make safety assessments on an ongoing basis. The Sponsor's medical monitor will review safety information from all study sites as it becomes available throughout the study. Should any safety concerns be identified, the Data Monitoring Committee (DMC) will be asked to review the data and determine what action is recommended.

## 10.2 Independent Data Monitoring Committee (DMC)

An independent DMC will be constituted for this study to monitor important aspects of study conduct, including safety results on an ongoing basis. The DMC will consist of 3 members who will be selected by the Sponsor but will be independent from the Sponsor. The clinicians on the committee will not participate in the study as Principal or Co-investigators, and should be isolated from the study if their institution is a study site. The DMC members

receive no financial incentives for their participation, but are reimbursed only for customary consultative and administrative support fees.

DMC meeting frequency and conduct is outlined in a separate DMC Charter. An independent unblinded statistician will provide the committee with masked data for review (treatment A versus treatment B), but will not be a member of the committee. All members of the DMC will treat study data, reports, meeting discussions, and conclusions as confidential.

The members of the DMC will not participate in the interim analysis and re-assessment of the sample size for this trial. This will be conducted by a separate Interim Analysis Committee as outlined in Section 9.9.

## **11 IEC/IRB APPROVAL**

The Principal Investigator agrees to provide the Independent Ethics Committee (IEC)/Institutional Review Board (IRB) with all appropriate material, including a copy of the informed consent. The study will not be initiated until the Investigator obtains written approval of the research plan (protocol) and the informed consent document from the appropriate IEC/IRB and copies of these documents are received by Nabriva Therapeutics AG.

It is the Investigator's responsibility to obtain IEC/IRB approval for all subsequent major changes to the protocol, in compliance with local law. Appropriate reports on the progress of this study will be made by the Investigator to the IEC/IRB and Sponsor in accordance with applicable government regulations and in agreement with policy established by the Sponsor.

## **12 ETHICAL CONDUCT OF THE STUDY**

This clinical study will be conducted in compliance with this Protocol, the guidelines of the World Medical Association Declaration of Helsinki in its revised edition (Fortaleza, Brazil, October 2013), the guidelines of International Conference on Harmonization (ICH) Good Clinical Practice (GCP) (CPMP/ICH/135/95), European Union (EU) Clinical Trials Directive 2001/20/EC, EU Commission Directive 2005/28/EC, and Code of Federal Regulation (CFR) Title 21, CFR Part 50, 56 and 312, designated Standard Operating Procedures, and with local laws and regulations relevant to the use of new therapeutic agents in the country of conduct.

## **13 INFORMED CONSENT**

The International Conference on Harmonization (ICH) has issued guidelines to provide protection for human subjects in clinical investigations. The ICH Tripartite Guideline for Good Clinical Practice establishes the general requirements for informed consent.

A properly executed, written informed consent in compliance with the terms of these guidelines shall be obtained from each subject before entering the study, or before performing any unusual or non-routine procedure in relation to the study. The purpose of the study, procedures to be carried out, and potential hazards will be described to each potential

subjects in non-technical terms. Subjects (or their legally authorized representative) will be required to read, voluntarily sign, and date an informed consent form summarizing the discussion at Screening, and will be assured that they may withdraw from the study at any time without jeopardizing their medical care.

Subjects (or their legally authorized representative) will sign and date 1 copy of the informed consent form which will be photocopied. The copy will be retained by the subject (or their legally authorized representative) and the original will be retained on file by the Investigator.

The consent form must be approved by the appropriate IEC/IRB and Sponsor before study initiation at a study site. Any subsequent changes to the approved informed consent form must be reviewed and approved by the appropriate IEC/IRB and Sponsor before implementation.

## **14 QUALITY ASSURANCE/QUALITY CONTROL**

Standard Operating Procedures belonging to Nabriva Therapeutic AG or designee(s) will be adhered to for all activities relevant to the quality of the study and are routinely monitored by the Quality Assurance (QA) Division.

Data will undergo quality control checks prior to clinical database lock. Sponsor-designated, independent monitors will be responsible for the monitoring of the study and its data within the eCRFs.

A QA audit of this study may be conducted by the Sponsor or Sponsor's designee. The QA auditor will have access to all medical records, the Investigator's study-related files and correspondence, and information in the informed consent documentation of this study.

An inspection of this study may be conducted by a regulatory agency. The Investigator agrees to contact the Sponsor as soon as possible, but not later than within 1 week, upon notification of an inspection by a regulatory agency. The Investigator agrees to allow the Inspector direct access to all relevant documents and to allocate his/her time and that of study site personnel to the Inspector to discuss findings in any relevant issues. The Investigator will allow Sponsor personnel to be present as an observer during a regulatory inspection, if requested.

## **15 DATA HANDLING AND RECORD KEEPING**

### **15.1 Data Handling**

Data will be recorded at sites using eCRFs and reviewed by the Sponsor or designee during monitoring visits. The recorded data in the EDC system will be verified with source documents. All corrections or changes made to any study data must be appropriately tracked in an audit trail in the EDC system. eCRFs will be considered complete when all missing, incorrect, and/or inconsistent data has been accounted for. Data collected at baseline will only be entered into the eCRF if the subject is eligible for study participation following review of the data by the Investigator or designee.

Adverse events, concomitant medication data and clinical observations will be in the subjects' hospital notes, or recorded on source data forms, and will be transferred into the eCRF after assessment by the Investigator or designee.

Data produced by automatic devices with original print-outs (e.g., clinical laboratory test results, ECG traces, BP measurements) will be included in the source documentation. Clinical laboratory parameters are to be reviewed, signed and dated by the Investigator or designee. Any results outside the normal range should be designated by the Investigator or designee as not clinically significant (NCS) or clinically significant (CS).

## 15.2 Subject Confidentiality

Investigator and his/her staff will be required to manage subject data collected for the study in accordance with applicable laws and regulations on personal data protection.

**US:** All US-based investigational sites and laboratories or entities providing support for this study, must, where applicable, comply with the Health Insurance Portability and Accountability Act (HIPAA) of 1996. An investigational site that is not a Covered Entity as defined by HIPAA must provide documentation of this fact to Nabriva Therapeutics AG.

**EU:** Data collected during this study may be used to support the development, registration or marketing of lefamulin. Nabriva Therapeutics AG will control all data collected during the study, and will abide by the EU Directive on Data Privacy concerning the processing and use of subjects' personal data. For the purpose of data privacy legislation, Nabriva Therapeutics AG will be the data controller.

After subjects have consented to take part in the study their medical records and the data collected during the study will be reviewed by Nabriva Therapeutics AG or its representatives. These records and data may, in addition, be reviewed by the following: independent auditors who validate the data on behalf of Nabriva Therapeutics AG; third parties with whom Nabriva Therapeutics AG may develop, register or market lefamulin; national or local regulatory authorities and the IRB/IECs that gave approval for this study to proceed.

Subjects will be known by a unique number; however, their date of birth can also be collected if not in contradiction with any requirements (e.g., from IECs) and used to assist Nabriva Therapeutics AG to verify the accuracy of the data, for example, that the laboratory results are assigned to the correct subject. The results of this study may be recorded and transferred to and used in other countries throughout the world, which may not afford the same level of protection that applies within the EU. The purpose of any such transfer would be to support regulatory submissions in other countries.

## 15.3 Computer Systems

Data will be processed using a validated computer system conforming to regulatory requirements.

## 15.4 Data Entry

Data must be recorded using the EDC system as the study is in progress. All study site personnel must log into the system using their secure user name and password in order to enter, review, or correct study data. These procedures must comply with the Title 21 Code of Federal Regulations (21 CFR Part 11) for US sites and EU Directives 2001/20/EC and 2005/28/EC for EU sites. All passwords will be strictly confidential.

## 15.5 Data Validation

Validation checks programmed within the EDC system as well as supplemental validation performed via review of the downloaded data will be applied to the data in order to ensure accurate, consistent, and reliable data. Data identified as erroneous, or data that are missing, will be referred to the investigative site for resolution through data queries.

eCRFs must be reviewed and electronically signed by the Investigator who signed the protocol.

## 15.6 Record Keeping

Raw data generated in connection with this study as well as an original copy of the final clinical study report, will be retained in archive until at least 5 years after the last approval of a marketing application in an ICH region and until there are no pending or contemplated marketing applications in an ICH region or at least 5 years have elapsed since the formal discontinuation of clinical development of lefamulin. These documents will be retained for a longer period if required by the applicable regulatory requirements or by an agreement with the Sponsor. It is the responsibility of the Sponsor to inform the Investigator/Institution as to when these documents no longer need to be retained.

As required under European Directive 2005/28/EC, Article 17, all 'essential documents' (as described in the ICH GCP Guidelines) must be retained by Nabriva Therapeutics AG and the Investigator for at least 5 years after the completion of the clinical study. Therefore all studies, independent of where they were conducted in the world, must follow this requirement in the event a submission is ever made in the EU. These documents may be retained for a longer period, however, if required by the applicable regulatory requirements or by an agreement with Nabriva Therapeutics AG. It is the responsibility of Nabriva Therapeutics AG to inform the Investigator as to when these documents no longer need to be retained. The Investigator must obtain written permission from Nabriva Therapeutics AG prior to the destruction of any study document.

The retention of investigator study records is an investigator responsibility and Nabriva Therapeutics AG will neither arrange nor pay for this activity. Any transfer of ownership of the content of the clinical trial master file is the responsibility of the investigator or site representative, and shall be documented. The new owner shall assume the responsibilities set forth in the applicable regulations.

These records must be made available at reasonable times for inspection and duplication, if required, by a properly authorized representative of the US Food and Drug Administration (FDA) in accordance with 21 CFR 312.68 or other national or foreign Regulatory Authorities in accordance with regulatory requirements.

## **16 TERMINATION OF STUDY**

The Sponsor reserves the right to discontinue this study at any time.

## **17 FINANCING AND INSURANCE**

The costs necessary to perform the study will be agreed with each Investigator and will be documented in a separate financial agreement that will be signed by the Investigator and Nabriva Therapeutics AG (or designee), prior to the start of the study. A statement regarding insurance/indemnity such as Association of British Pharmaceutical Industry (ABPI) should also be included.

The Investigator will be required to disclose any financial arrangement whereby the value of the compensation for conducting the study could be influenced by the results or outcome of the study. The following information will be collected: any significant payments of other sorts from Nabriva Therapeutics AG, (e.g., money to fund ongoing research, compensation in the form of equipment, retainer for ongoing consultation or honoraria); any proprietary interest in lefamulin; any significant equity interest in Nabriva Therapeutics AG as defined in 21 CFR 54 2(b).

In consideration of participation in the study, Nabriva Therapeutics AG will pay the Investigator or nominated payee the sums set out in the payment schedule attached to the Investigator agreement.

## **18 PUBLICATION POLICY**

It is intended that the results of the study may be published as scientific literature. Results may also be used in submissions to Regulatory Authorities. The following conditions are to protect commercial confidential materials (e.g., patents, etc.), not to restrict publication.

All information concerning lefamulin (such as patent applications, formulae, manufacturing processes, basic scientific data, or formulation information supplied to the Investigator by Nabriva Therapeutics AG and not previously published) is considered confidential by Nabriva Therapeutics AG and shall remain the sole property of Nabriva Therapeutics AG. The Investigator agrees not to use it for other purposes without Nabriva Therapeutics AG written consent.

It is understood by the Investigator that Nabriva Therapeutics AG will use the information developed in this clinical study in connection with the development of lefamulin and, therefore, may be disclosed as required to other Nabriva Therapeutics AG Investigators or any appropriate international Regulatory Authorities. In order to allow for the use of information derived from this clinical study, the Investigator understands that he/she has an

obligation to provide Nabriva Therapeutics AG with complete test results and all data developed during this study.

All manuscripts, abstracts or other modes of presentation arising from the results of the study must be reviewed and approved in writing by Nabriva Therapeutics AG in advance of submission. The review is aimed at protecting Nabriva Therapeutics AG's proprietary information existing either at the date of the commencement of the study or generated during the study.

The detailed obligations regarding the publication of any data shall be set out in the agreement between each Investigator and Nabriva Therapeutics AG.

## 20 APPENDICES

1. Clinical Laboratory Tests (Safety)
2. Short Acting Antibiotics
3. Closely Monitored CYP3A4 Substrates and P-Glycoprotein Substrates (excluding strong CYP3A inducers and inhibitors and excluding strong P-glycoprotein inhibitors)
4. Prohibited Strong P-Glycoprotein Inhibitors and Strong CYP3A Inducers and Inhibitors
5. Drugs That Prolong QT
6. High Tyramine Diet

## **Appendix 1      Clinical Laboratory Tests (Safety)**

Blood and urine samples for the following laboratory tests will be sent to a central laboratory for testing.

### **Hematology**

Complete blood count (CBC) with RBC indices and WBC differential

Platelet count

### **Chemistry**

BUN

Creatinine

Glucose

Sodium

Potassium

Chloride

Calcium

Magnesium

Phosphorus

AST

ALT

GGT

Alkaline Phosphatase

CPK

Total Bilirubin

Direct Bilirubin

Uric Acid

Albumin

Total Protein

### **Urinalysis**

Specific gravity

pH, glucose, protein, blood, ketones, bilirubin and leukocyte esterase by dipstick

Microscopic examination (all samples)

### **Other tests**

Procalcitonin

### **Tests at Screening Only**

Serum pregnancy test

Urine pregnancy test (testing kit provided by central laboratory; test to be performed at the local site prior to randomization)

## Appendix 2 Short Acting versus Long Acting Antibiotics

Short-acting	Long-acting
Cephalosporins	
Cefaclor, Cefadroxil, Cefdinir, Cefepime, Cefixime (200 mg), Cefotaxime, Cefpodoxime, Cefprozil, Ceftazidime, Ceftibuten, Cefditoren, Cefruoxime, Cephalexin, Loracarbef	Cefixime (400 mg), Ceftriaxone
Fluoroquinolones	
Ciprofloxacin, Norfloxacin	Gatifloxacin, Gemifloxacin, Grepafloxacin, Levofloxacin, Moxifloxacin, Sparfloxacin
Macrolides and Ketolides	
Clarithromycin, Erythromycin, Roxithromycin	Azithromycin, Clarithromycin XL (extended release), Dirithromycin, Telithromycin
Penicillins and Carbapenems	
Amoxicillin, Amoxicillin-Clavulanate, Amoxicillin-Sulbactam, Ampicillin, Ampicillin-Sulbactam, Dicloxacillin, Imipenem, Meropenem, Nafcillin, Oxacillin, Penicillin-G, Penicillin-V, Piperacillin, Piperacillin-Tazobactam, Ticarcillin-Clavulanate	Ertapenem, Penicillin-G, Benzathine/Procaine
Tetracyclines	
Doxycycline (100 mg), Minocycline, Tetracycline	Doxycycline (200 mg), Minocycline Extended Release

**Appendix 3 Closely Monitored CYP3A4 Substrates and P-Glycoprotein Substrates (excluding strong CYP3A inducers and inhibitors and excluding strong P-glycoprotein inhibitors)**

Closely Monitored CYP3A4 Substrates		
Alfentanyl	Efavirenz	Pimozide
Alprazolam	Eplerenone	Progesterone
Amiodipine	Estradiol	Propranolol
Aprepitant	Fentanyl	Quetiapine
Aripiprazole	Finasteride	Quinine
Astemizole	Gleevec	Reserpine
Buspirone	Haloperidol	Salmeterol
Cafegot	Hydrocortisone	Sildenafil
Caffeine	Lercanidipine	Sirolimus
Chlorpheniramine	Lidocaine	Terfenadine
Cilostazol	Methadone	Testosterone
Cocaine	Midazolam	Trazodone
Codeine	Nateglinide	Triazolam
Dapsone	Nevirapine	Zaleplon
Dexamethasone	Nifedipine	Ziprasidone
Dextromethorphan	Nisoldipine	Zolpidem
Docetaxel	Nitrendipine	
Domperidone	Ondansetron	

Closely Monitored P-Glycoprotein Substrates		
Apixaban	Fexofenadine	Ranitidine
Carvedilol	Fosamprenavir	Rivaroxaban
Cimetidine	Ivermectin	Saxagliptin
Colchicine	Ledipasvir	Silodosin
Dabigatran	Loperamide	Sitagliptin
Daclatasvir	Losartan	Sofosbuvir
Dasabuvir	Maraviroc	Tetracycline
Dexamethasone	Methylprednisolone	Tipranavir
Digoxin	Methotrexate	Tolvaptan
Domperidone	Morphine	Umeclidinium
Edoxaban	Ombitasvir	Vecuronium
Empagliflozin	Paliperidone	Vilanterol
Estradiol	Paritaprevir	
Ezetimibe	Prazosin	

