### 6.7.2 Concomitant Medication

All concomitant medications taken during the study will be recorded in the subject's eCRF.

In the case that additional antibiotic treatment is required for the current episode of CABP, the subject's study drug will be discontinued and they will be considered to have an IACR of Failure; however, subjects will continue to be followed for safety as detailed in Section 6.17.1.

Although all drugs that are metabolized by CYP3A4 are not prohibited, they should only be used when necessary and with appropriate subject monitoring. *In vitro* studies demonstrated that lefamulin may inhibit the metabolism of substrates of CYP3A4; however, results obtained from Phase 1 drug interaction studies performed demonstrate that lefamulin has a marginal effect on CYP3A4 inhibition in humans and no change in lefamulin's dose is required. In addition, all drugs that are P-glycoprotein substrates are not prohibited; however, they should only be used when necessary and with appropriate subject monitoring. A list of drugs that are CYP3A4 substrates and P-glycoprotein substrates is provided in Appendix 3.

Close monitoring is recommended in subjects who require medication that can reduce potassium levels (e.g., loop and thiazide-type diuretics, laxatives and enemas [high doses], corticosteroids, amphotericin B) or medication that is associated with clinically significant bradycardia.

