## 6.8 Prohibited Medications

The following medications are prohibited:

- Prior (within 72 hours before randomization) oral or IV antibacterials for CABP.
  - NOTE: Up to 25% of subjects may have a single dose of a short acting antibiotic for the current episode of CABP within 24 hours of randomization.
  - EXCEPTION: A subject who has received >48 hours of prior systemic antibacterial therapy for the current episode of CABP with unequivocal evidence of treatment failure (i.e., worsening signs and symptoms) and the isolation of an organism from blood or respiratory tract that is resistant to the prior systemic antibacterial therapy, providing the organism is not resistant to fluoroquinolones and, in the case of MRSA, oxazolidinones.
- Agents that prolong the QT interval (see Appendix 5)

- Other systemic antibacterial agents that are potentially effective against pathogens associated with CABP except in the case of treatment failure or when medically necessary for treatment of a concomitant infection.

**NOTE:** The following antibacterial agents are permitted:

- Anti-tuberculosis drugs (exception: Rifampin)
  - Cinoxacin
  - Dapsone
  - Enoxacin
  - Fidaxomicin
  - Methenamine Mandelate
  - Metronidazole
  - Naladixic Acid
  - Nitrofurantoin
  - Norfloxacin
  - Oral Vancomycin
- Systemic corticosteroids at a dose  $\geq 20$  mg per day (prednisone equivalent)
  - Anti-epilepsy or seizure medication
  - Strong p-glycoprotein inhibitors and strong CYP3A inhibitors or inducers (see Appendix 4). [NOTE: The use of contraceptives containing progesterone is not permitted.]
  - Monoamine oxidase inhibitors, serotonergic agents or adrenergic agents (dobutamine, dopamine, epinephrine, norepinephrine, phenylpropanolamine, pseudoephedrine) (only for subjects in whom linezolid is added for MRSA).

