## Appendix 4 Prohibited Strong P-Glycoprotein Inhibitors and Strong CYP3A Inducers and Inhibitors

Prohibited Strong P-Glycoprotein Inhibitors		
Amiodarone	Indinavir	Ranolazine
Atorvastatin	Itraconazole	Reserpine
Boceprevir	Ketoconazole	Ritonavir
Bromocriptine	Linagliptin	Saquinavir
Captopril	Lopinavir and ritonavir	Simeprevir
Carvedilol	Lovastatin	Simvastatin
Cobicistat	Meperidine	Suvorexant
Conivaptan	Methadone	Tacrolimus
Cyclosporine	Nelfinavir	Tamoxifen
Diltiazem	Nicardipine	Telaprevir
Doxazosin	Pentazocine	Ticagrelor
Dronedarone	Progesterone	Verapamil
Felodipine	Quercetin	
Fluvastatin	Quinidine	

Prohibited Strong CYP3A Inhibitors	Prohibited Strong CYP3A Inducers
Indinavir	Carbamazepine
Nelfinavir	Phenobarbital
Ritonavir	Phenytoin
Itraconazole	Pioglitazone
Ketoconazole	Rifabutin
Nefazodone	Rifampin
Saquinavir	St. John's Wort
Suboxone	Troglitazone

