## Appendix 5      Drugs That Prolong QT

Anticonvulsants	Fosphenytoin; Felbamate
Antihistamines	Azelastine, Clemastine
Anti-Infectives	Amantadine, Clarithromycin, Chloroquine, Foscarnet, Erythromycin, Halofantrine, Mefloquine, Pentamidine, Sparfloxacin, Quinine, Trimethoprim-Sulfamethoxazole, Ketoconazole
Antineoplastics	Tamoxifen
Cardiovascular	
Antiarrhythmics	Amiodarone, Bretylium, Disopyramide, Flecainide, Ibutilide, Procainamide, Quinidine, Sotalol, Dofetilide
Calcium Channel Blockers	Bepriidil, Israpidine, Nicardipine
Diuretics	Indapamide, Moexipril/ hydrochlorothiazide
Hormones	Octreotide, Vasopressin
Immunosuppressives	Tacrolimus
Migraine: Serotonin Receptor Agonists	Zolmitriptan, Naratriptan, Sumatriptan
Muscle Relaxants	Tizanidine
Narcotic Detoxification	Levomethadyl
Psychotherapeutics	
Antidepressants	Amitriptyline, Desipramine, Fluoxetine, Imipramine, Venlafaxine
Antipsychotics	Chlorpromazine, Haloperidol, Pimozide, Quetiapine, Risperidone, Thioridazine
Antianxiety	Doxepin
Antimanic	Lithium
Respiratory (Sympathomimetics)	Salmeterol
Sedative/Hypnotics	Chloral hydrate

Note: List not exhaustive.

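### Four drugs that Appendix 4 prohibits as strong P-glycoprotein inhibitors are also in Appendix 3 as closely monitored substrates, and five Appendix 5 QT drugs overlap with Appendix 3 unflagged, with no rule on which list governs

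*Protocol*

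**What the plan says.** Section 6.7.2 (Concomitant Medication) sets the status of two metabolic classes. On CYP3A4 it says: "Although all drugs that are metabolized by CYP3A4 are not prohibited, they should only be used when necessary and with appropriate subject monitoring". On P-glycoprotein it says that "all drugs that are P-glycoprotein substrates are not prohibited; however, they should only be used when necessary and with appropriate subject monitoring". It then sends the site to a list: "A list of drugs that are CYP3A4 substrates and P-glycoprotein substrates is provided in Appendix 3".

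The Appendix 3 heading limits that list. It is compiled "excluding strong CYP3A inducers and inhibitors and excluding strong P-glycoprotein inhibitors".

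Appendix 4 is titled "Prohibited Strong P-Glycoprotein Inhibitors and Strong CYP3A Inducers and Inhibitors". Section 6.8 prohibits its drugs during the study, and Exclusion 9 in Section 4.2 makes receiving one a bar to entry.

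Appendix 5 lists QT-prolonging drugs, among them the antipsychotics "Chlorpromazine, Haloperidol, Pimozide, Quetiapine, Risperidone, Thioridazine", and notes that it is not complete. Section 6.8 prohibits these agents. Exclusion 8 bars subjects who received such a drug in the 7 days before enrollment or who, in the investigator's opinion, may need one during the study.

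Amendment 3 was issued because progesterone's place in Appendix 4 conflicted with the contraception criterion. It changed Inclusion 8 and Section 6.8. Progesterone is still in the current Appendix 3.

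**The concern.** A monitoring list and a prohibition list work only if a drug can be looked up and given one answer. Appendix 3 presents itself as already cleared of strong P-glycoprotein inhibitors, so a reader who finds carvedilol there has reason to think it is not one. Appendix 4 says that it is.

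The lists bear on risks that the protocol itself describes. Section 1.4 identifies lefamulin as a P-glycoprotein substrate. Section 1.5.3 reports reproducible, concentration-dependent QT prolongation. Section 6.17.3 sets QTcF criteria for withdrawal from treatment. Section 3 plans approximately 125 centers, so the same drug may be looked up by many different people. At stake are concomitant-medication decisions during treatment and consistent recording of protocol deviations. No sample size, power or error rate is involved.

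**Working it through.** The protocol gives no figure to reproduce. The check compares the printed lists by exact drug name.

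**Inputs**
- Appendix 3: 52 CYP3A4 substrates and 40 P-glycoprotein substrates. Three names (dexamethasone, domperidone, estradiol) are in both tables, so there are 52 + 40 − 3 = 89 distinct drugs.
- Appendix 4: 40 strong P-glycoprotein inhibitors, 8 strong CYP3A inhibitors and 8 strong CYP3A inducers. Six inhibitors are listed in two tables, so there are 40 + 8 + 8 − 6 = 50 distinct drugs.
- Appendix 5: 54 drugs.

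**Overlaps**

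| Drug | Place in Appendix 3 | Place on a prohibited list | Rules that prohibit it |
|---|---|---|---|
| Carvedilol | P-glycoprotein substrates | Appendix 4, strong P-glycoprotein inhibitors | Section 6.8, Exclusion 9 |
| Methadone | CYP3A4 substrates | Appendix 4, strong P-glycoprotein inhibitors | Section 6.8, Exclusion 9 |
| Progesterone | CYP3A4 substrates | Appendix 4, strong P-glycoprotein inhibitors | Section 6.8, Exclusion 9 (contraceptives also in Inclusion 8) |
| Reserpine | CYP3A4 substrates | Appendix 4, strong P-glycoprotein inhibitors | Section 6.8, Exclusion 9 |
| Haloperidol, pimozide, quetiapine | CYP3A4 substrates | Appendix 5, antipsychotics | Section 6.8, Exclusion 8 |
| Quinine | CYP3A4 substrates | Appendix 5, anti-infectives | Section 6.8, Exclusion 8 |
| Salmeterol | CYP3A4 substrates | Appendix 5, respiratory | Section 6.8, Exclusion 8 |

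Appendices 3 and 4 share 4 drugs, and Appendices 3 and 5 share 5. No drug is in both overlaps, so the total is 4 + 5 = 9 distinct drugs.

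**The two groups differ in kind**
- The first four contradict the Appendix 3 heading. The heading says that strong P-glycoprotein inhibitors were left out, and Appendix 4 classes all four as exactly that.
- The other five do not contradict the heading, which is silent on QT drugs. A drug can be a CYP3A4 substrate and also prolong QT. What is missing is any sign in Section 6.7.2 or Appendix 3 that these entries are prohibited on another ground.

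No section says which list prevails when a drug is in more than one.

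**The case against.** The strongest reply is that the bans are not in doubt. Exclusion 9 cites only Appendix 4, and Exclusion 8 cites only Appendix 5. Section 6.8 cites only those two appendices for these classes. In the operative text Appendix 3 is cited only from Section 6.7.2, and it is not worded as an exemption. On this reading the restrictions add up and all nine drugs remain prohibited. That stands. A reader might infer that the protocol permits enrollment on these drugs, but the entry criteria do not support this.

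The reply is also right that the heading is contradicted by four drugs, not nine. For progesterone contraceptives, Inclusion 8 and Section 6.8 state the rule outright, so what remains is an uncorrected Appendix 3 entry.

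The safety weight should not be overstated. Section 1.5.1 does not expect interactions with potent CYP3A and P-glycoprotein inhibitors to justify a dose adjustment, and the protocol requires triplicate ECGs and has QTcF stopping criteria. The documents nowhere say that both prohibited lists exist to prevent raised lefamulin exposure, and Appendix 4 also contains inducers, which that reason would not explain.

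Two further inferences are tempting. A reader might see a conflict over rifabutin, because Section 6.8 allows anti-tuberculosis drugs except rifampin while Appendix 4 prohibits rifabutin. The documents do not class rifabutin as an anti-tuberculosis drug, and the allowance is a note to a different bullet. A reader might also expect some of the nine drugs to be common in this population, but the protocol gives no usage data.

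The reply does not remove the contradiction in the heading or supply a precedence rule.

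**Conclusion.** The point holds in a limited form. Four drugs have two incompatible placements, against Appendix 3's own heading. Five more are on both the monitoring list and the QT list without a flag. The prohibitions remain in force, so this is a defect in the instructions to sites and not a loosening of eligibility. A site that relies on Section 6.7.2 and Appendix 3 could start or continue a prohibited drug, and sites could differ on whether that is a deviation.

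The count of nine rests on exact matching of printed names. Because Appendix 5 describes itself as incomplete, the overlap between Appendix 3 and QT-prolonging drugs could be larger, but the documents do not show by how much. The number of subjects affected cannot be estimated from the protocol. No effect on randomization, endpoints or the analysis is shown. The correction is worth making because it is specific and cheap, and because it concerns P-glycoprotein interaction and QT effects, both of which the protocol raises itself.

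**What to change.** Reconcile Appendices 3, 4 and 5 with Sections 6.7.2 and 6.8 so that each of the nine drugs has one status. Check the remaining entries at the same time. State which list governs when a drug is in more than one, and repeat that rule in Section 6.7.2 and under the Appendix 3 heading. Notify sites, so that medication decisions and deviation coding follow one rule. Which status is right for each drug is for the sponsor's clinical team, and this review takes no view on it.

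The cost is an appendix and text correction plus a site notice. Design, sample size and analysis are unchanged.
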